Annex 3- FDI (World Dental Federation) criteria	
Annex 4- USPHS (Modified U.S Public Health Service) criteria	32

TABLES INDEX

1 - INTRODUCTION

Historically, dental adhesives have been broadly divided into total-etch (TE), etch-andrinse (ER) and self-etch (SE) adhesives (1–3). Total-etch are considered the goldstandard adhesive systems on enamel bonding rendering the most pronounced etch patterns on cut and uncut enamel.

Self-etching adhesive systems, or "*self-etch*"(*SE*) as are usually called, were developed in the beginning of years ninety, with main purpose to simplify, even more, the clinical steps comparatively with the available adhesive systems (ER) in the market. SE primers are systems constituted by an acidic primer and a fluid resin and SE adhesives function as all-in-one systems, as a solution that demineralised and impregnates the resin in the demineralised layer, in only one step (1,4,5). SE adhesives use acidic monomers, with different pH values, to demineralise/modify dentin and enamel patterns while, simultaneously, primers/resins infiltrate into demineralised tissues and dentin tubules (6).

Few data exists with respect to mean and long-term observational clinical performance of SE all-in-one adhesive systems (7). However, their clinical use is increasing (8), contributing to this growth the fact of being user-friendlier (shorter application time, less clinical steps), less technique-sensitive (no wet-bonding, simple drying), and the perception that SE adhesives cause less postoperative sensitivity than ER adhesives. This argument is manly supported by their less aggressive (when compared to phosphoric-acid pH value) regarding acidity and, thus more superficially interaction with dentin occurs, leaving tubules largely obstructed with smear layer (6). However, some of those factors are controversial regarding some clinical outputs (9). SE adhesives would result in poorer enamel marginal integrity than TE/ER adhesives, since the integrity and durability of the enamel bond, particularly to uncut enamel, is the weak link for these materials. One-step SE adhesives showed higher bond strengths on ground enamel and no reductions in resin-enamel bonds were observed after 12 months of water storage. Marginal adaptation was significantly better for Clearfil S3 Bond than for Adper Prompt L-Pop, according to *in vitro* findings (10).

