Multimode one-bottle universal adhesives have been developed recently to make the clinical procedure even more user-friendly. These systems can be used for both direct and indirect restorations (16) and provide the flexibility for the clinician to select and choose the adhesive use mode (ER or SE) according to the clinical and dental hard tissues conditions. From a marketing perspective MM adhesives are highly innovative products offering the clinician the liberty of adapting a single-bottle SE adhesive for use as ER mode or as selective enamel etching (SE-EE) adhesion mode without compromising its bonding effectiveness (17). Controversy remains on, if these versatile adhesives contain technological advances for overcoming challenges associated with previous generations of adhesives or adhesion modes, since the available data mainly is based on in vitro findings. The concept behind these adhesives is novel; hence, only few short/mean-term clinical (16,18-20) and, immediate ultra-morphological and bond strength studies (21-25) have been reported. Some laboratory findings revealed that performance of universal multimode adhesives was shown to be material-dependent (23). Despite being considered user-friendly, acidity adjustment of MM adhesive solutions and incorporation of new functional monomers to promote clinical performance stability over time were the main changes proposed to improve these materials. Perdigao and colleagues observed during 18th month the clinical performance of the MM adhesive, Scotchbond Universal Adhesive (3M ESPE, St Paul, MN, USA) in non-carious cervical lesions (NCCLs) and concluded that, restorations retention with this universal adhesive was not dependent on the bonding strategy. Differences between use modes were detected only for adhesive restorations marginal adaptation, by FDI criteria (World Dental Federation- clinical criteria for direct/indirect restorations evaluation), but not by the USPHS (United States Public Health Service) criteria (16). Controversy remains about the use of MMP inhibitors to control the degradation of dentin-resin interfaces (26). According to the adhesion-decalcification (A-D) concept aggressive demineralization of hard tissues by strong acids results in dissolution of apatite crystallites, decreasing the opportunity to establish chemical bonds between SE

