H0 – Bonding to NCCLs with FBDC-SE (G1) and MM-SE(G4G6) result in similar restorations (aesthetic, functional and biologic) success rates;

H0 – Bonding to NCCLs with FBDC-SE (G1) and MM-SE (G4G6) adhesives result in similar restoration retention rates;

H0 – Bonding to NCCLs with FBDC by SE and enamel etching mode (FBDC-SE-EE; G2) and MM adhesives by Etch-and-Rinse mode (MM-ER; G3G5) result in similar (no significant differences) clinical (aesthetic, functional and biologic) behaviour/performance;

H0 – Bonding to NCCLs with FBDC-SE-EE (G2) and MM-ER (G3G5) result in similar restorations (aesthetic, functional and biologic) success rates;

H0 – Bonding to NCCLs with FBDC-SE-EE (G2) and MM-ER (G3G5) result in similar restoration retention rates;

H0 – Bonding to NCCLs with FBDC (G1G2) or FBU (G3G4), DC adhesives, and ADU (G5G6) light-curing adhesive, with SE or SE-ER/ER modes result in similar (no significant differences) clinical (aesthetic, functional and biologic) behaviour/performance;

H0 – Bonding to NCCLs with FBDC (G1G2) or FBU (G3G4) and ADU (G5G6) lightcuring adhesive, with SE or SE-ER/ER modes result in similar restorations (aesthetic, functional and biologic) success rates;

H0 – Bonding to NCCLs with FBDC (G1G2) or FBU (G3G4) and ADU (G5G6) lightcuring adhesive, with SE or SE-ER/ER modes result in similar restoration retention rates;

H0 - FDI or USPHS criteria evaluation outcomes not differ for the same data, at 24th month follow-up.

2 – POPULATION, MATERIALS AND METHODS

2.1- TRIAL DESIGN

The trial design follows the Consolidated Standards of Reporting Trials (CONSORT) statement (30). Prospective, double blind, clinical trial; randomized allocation of NCCL restorations by six adhesion interventional groups (6 arms) for examination of restorations performance.

Study will take place in University

Dentistry School Clinic. Participants recruitment between November 2015 and April 2016. Restorations estimated to be done until April or May 2016 year.

-

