Study variable definition_- Clinical/direct observation and performance evaluation acceptance by means of FDI (*FDI World Dental Federation - clinical criteria for the evaluation of direct restorations*) (Adapted from (33) (Annex 3) and USPHS (34) (Annex 4).

2.7- DATA AND STATISTICAL ANALISYS PLAN (SAP)

Data statistical analysis and description according to aims of this trial; Specific program for statistical data analysis (IBM(c) SPSS(c) Statistics vs. 22 or later) will be used. The changes in parameters clinical performance (paired comparison analysis) by both, FDI and USPHS criteria will be assessed by McNemar or Wilcoxon tests, for both

primary and secondary outcomes, to determine differences between treatments with regard to aesthetic, functional and biological parameters from baseline to 24th month recall (longitudinal assessment). Differences will be considered to be significant at P<0.05. Whenever 3 groups will be compared at 24 months' recall, a Kruskal Wallis test will be used and upon significant differences detection, then Mann-Whitney tests considering Bonferroni correction will be used for pairwise group comparisons.

Comparison of FDI and USPHS acceptance (success rate) criteria evaluation outcomes for Esthetic, for Functional and for Biological Parameters, at 24th Month Follow-up, were compared using the chi-square test.

If missing data occurs, that is, if dropouts or non-observed due to loss of retention of the restoration, then the paired comparison will consider for the baseline just the restorations existing at the last moment (24 months).

2.8- OBSERVATIONS REGARDING SAMPLE CALCULATION

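### Free improvement: the product comparison merges each product's unetched and etched arms without adjusting for mode, which costs some power where mode affects the outcome

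*Combined protocol and SAP*

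**What the plan says.** All places are in the combined protocol and SAP.

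- **Objectives and Hypothesis.** The seventh to ninth nulls, in listed order, concern "FBDC (G1G2) or FBU (G3G4), DC adhesives, and ADU (G5G6) light-curing adhesive, with SE or SE-ER/ER modes". They cover clinical performance, success rates and retention; the ninth, after naming FBDC (G1G2), continues "FBU (G3G4) and ADU (G5G6) lightcuring adhesive, with SE or SE-ER/ER modes result in similar restoration retention rates". Each product is written as a pair of arms, one unetched and one etched.
- **Section 2.7.** "Whenever 3 groups will be compared at 24 months' recall, a Kruskal Wallis test will be used", and after a significant result "Mann-Whitney tests considering Bonferroni correction will be used for pairwise group comparisons". The threshold is "Differences will be considered to be significant at P<0.05". No stratum, covariate or product-by-mode term is named.
- **Sections 2.2 and 2.8.** There are 210 envelopes in 35 sequences of six arms, so 35 restorations per arm and a planned 1:1 split of modes within each product. A participant may contribute one to six teeth, with no arm repeated. No power analysis was done.
- **Section 1 (Introduction).** On mode, the plan expects that "SE adhesives would result in poorer enamel marginal integrity than TE/ER adhesives". It also cites an 18-month clinical study of a universal adhesive: "Differences between use modes were detected only for adhesive restorations marginal adaptation". That study saw the difference by FDI but not by USPHS criteria, and its retention did not depend on bonding strategy.

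**The concern.** Mode is a randomised factor crossed with product. If it shifts the outcome, the 35 unetched and 35 etched restorations of one product come from two different distributions. An ordinary rank test on the merged 70 treats the gap between them as random variation within the product. The reference variance is then too large, the test rejects a true null less often than 5%, and real product differences are harder to detect.

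This matters because the sample size was not set by a power calculation, and because the nulls are phrased as similarity, so a non-significant result may be read as evidence that the products perform alike. Marginal adaptation, where the plan itself expects mode to act, is scored under both criteria (Annexes 3 and 4) and so feeds the seventh and eighth nulls.

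**Working it through.** **Plan's own figure.** 6 arms × 35 = 210, and 35 sequences × 6 = 210. Each product therefore has 70 restorations, 35 per mode. No power figure is given for these nulls. All effect sizes below are assumptions.

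**Five-grade score.** Inputs: proportional odds; base grade proportions 0.45, 0.30, 0.15, 0.06, 0.04; 35 per arm; one product differing by a log odds ratio of 0.8; independent teeth; 40,000 simulated trials per scenario. Kruskal-Wallis on 3 × 70 is compared with the van Elteren test in two mode strata of 3 × 35.

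| Mode log odds ratio (odds ratio) | Power %, merged v stratified, shifts to better grades | Same, shifts to worse grades | True size of merged test (better; worse) |
|---|---|---|---|
| 0 | 70.6 v 70.6 | 77 v 76 | – |
| 0.5 (1.65) | 65.7 v 66.5 | gain about 1 | about 4.75% |
| 1.0 (2.7) | 58.4 v 61.4 | 74 v 77 | 4.0%; 3.8% |
| 1.5 (4.5) | 49.7 v 56.1 | 69 v 78 | 3.1%; 3.0% |
| 2.0 (7.4) | 40.9 v 51.2 | 62 v 77 | 2.5%; 1.8% |

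The stratified test held 4.8–5.1%. A further run gave gains of about 1, 4, 8 and 16 points at 0.5, 1.0, 1.5 and 2.0.

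**Retention.** With modes 1:1 and a mode gap *d* around mean rate *p*, true variance ÷ variance assumed by the merged test = 1 − *d*²/[4*p*(1 − *p*)]. On two degrees of freedom the large-sample size is 0.05^(1/ratio). Example, 85% unetched and 95% etched: 1 − 0.01/(4 × 0.90 × 0.10) = 1 − 0.01/0.36 = 0.972, and 0.05^(1/0.972) = 4.6%. Power below is for one product 15 points lower (200,000 runs; the stratified test is Cochran-Mantel-Haenszel).

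| Unetched/etched % | Ratio | Size, large-sample | Size, simulated | Power %, merged v stratified |
|---|---|---|---|---|
| 90/90 | 1 | 5.0% | 4.6% | 70.6 v 70.6 |
| 90/95 | 0.991 | 4.9% | 4.6% | 77.1 v 77.6 |
| 85/95 | 0.972 | 4.6% | 4.3% | 70.7 v 71.9 |
| 80/95 | 0.949 | 4.3% | 4.0% | 65.2 v 67.1 |
| 75/95 | 0.922 | 3.9% | 3.7% | 60.8 v 64.0 |

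**Unequal losses, no product difference, five-grade score.** Capped at 35 per arm, analysed numbers of 30/30/35 unetched and 35/35/30 etched gave a merged size of 3.1–5.0%; 28/28/35 and 35/35/28 gave 4.6–5.0%. Clear excess appeared only with about 10 of 35 lost in opposed arms: about 6% at a mode log odds ratio of 1.0.

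**Participant correlation.** With 35 participants each giving six teeth and no mode effect, ignoring the correlation lowers size to about 3.4% at correlation 0.2 and 1.4% at 0.4. Stratifying by mode does not restore it: 2.8–3.4% and 1.1–1.5% over the mode shifts tried.

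**Interaction.** With assumed unetched/etched retention of 80/95, 90/90 and 95/80 in the three products, the product averages are 87.5, 90 and 87.5. Merged and stratified tests both reject only about 6% of the time.

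**The case against.** The strongest reply is that this is a refinement, not an error. For retention the plan's own cited study found no dependence on mode, and without a mode effect the two tests agree. Even for margins, that study saw a difference by only one of the two criteria. Losses become large only at odds ratios of about 4.5 to 7.4 between modes, which nothing in the documents supports. The first six nulls already compare FBDC with the multimode adhesives within each mode. All of this stands, and it limits the size of the point. It does not remove it: the first six nulls as worded merge FBU with ADU, so they do not separate all three products, and the adjustment costs nothing.

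Two further replies also stand. Section 2.7 speaks of any three-group comparison without naming these nulls, and the seventh can be read as dual-cure (G1 to G4) against light-curing (G5G6). And the participant is a blocking factor that the test also ignores; mode strata alone leave that untouched.

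A reader might infer that merging inflates false positives or biases the product contrast. The documents do not support that. The 210 envelopes supply 35 per arm, losses can only reduce that number, and under the planned 1:1 split the error is on the conservative side.

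**Conclusion.** The point holds as a free improvement. On the seventh to ninth nulls the planned test is conservative and loses some power wherever mode affects the outcome. The background supports that for marginal adaptation and not for retention. On a five-grade score the loss is about 1, 3–4 and 6–9 points of power at mode log odds ratios of 0.5, 1.0 and 1.5, with true size about 3–4% at 1.0–1.5. For retention it is 0–2 points for mode gaps up to 15 points. These figures assume independent teeth, the stated grade distribution and product effects, and the planned arm sizes; the documents quantify none of the effects.

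It would go too far to call the product comparison invalid, to expect a material loss on retention, or to say that mode strata alone secure a 5% test. Error clearly above 5% needs large losses running in opposite directions between modes, and teeth from one participant remain correlated after stratification.

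**What to change.** In section 2.7, name the test for the seventh to ninth nulls and their pairwise follow-up: an ordinal model for graded scores and a logistic model for success and retention, each containing product and mode, with participant as a GEE cluster or random effect. The mode sets are G1, G4, G6 and G2, G3, G5, as the first six nulls already use. Keep the Bonferroni correction for the pairs. A van Elteren or Cochran-Mantel-Haenszel test stratified by mode is a simpler alternative, but it does not handle the correlation between teeth.

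Report a product-by-mode check and the by-mode results beside the pooled result. Note there that the etched set combines selective enamel etching (G2) with etch-and-rinse (G3, G5), so mode is not identical across products. State whether the seventh to ninth nulls compare three products or dual-cure with light-curing.

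The cost is SAP wording and a little more analysis work. Design, sample size and data collection are unchanged, and nothing is lost if mode has no effect.

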The study is scheduled to last 24th months. Baseline clinical observation will be done 30 days after placement of adhesion restoration (First data research); a second appointment after 12th months (second data; data not to be included on final report, according to the main purpose and trial hypothesis to study) and the last research evaluation will be at 24th months after baseline (Final data/report). Clinical trial may continue for similar assessment intervals, after 24th months evaluation. This situation requires new analysis according to the clinical and economics conditions, at that time.

2.2- POPULATION AND PARTICIPANT SELECTION

All participants will be informed (Written and verbal Inform Consent, Annex 1) about the trial conditions and purposes, but will not be aware of what tooth will received the adhesion treatment strategy under evaluation. Written informed consent form (Annex 1), according to World Medical Association Declaration of Helsink (31), will be obtained from all participants prior to starting the treatment. University

Ethics Committee review and approved the present protocol. This clinical trial is done according to the European Union law for clinical research and National Law for Clinical Research (Law 21/2014, of 16 April), and was analysed, approved and authorized by the National Competent Authorities

- **CNPD**, Portuguese Data Protection Authority (Authorization and registry 6430/2015 at 7 July 2015; Case 2536/2015).
- **CEIC**, National Ethics Committee for Clinical Research (N.º 20150305; Approved at 3th August 2015)
- INFARMED, National Authority of Medicines and Health Products, IP (N.° EC/011/2015; DPS/DM/450.10.053/2015/0314; Authorization at 4th August 2015)

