In this study will be included participants with clinical diagnosis of tooth structure coronal loss and needs for cervical (vestibular surface) restoration without chemical or bacterial origin, called non-carious cervical lesion (NCCL) located in pre-molars/molars (PM/M) teeth, with cavity dimensions defined in the study design. Therefore, restorations can be made in PM or M teeth; a participant can have up to 16 teeth (8PM + 8M) with NCCL. The number of teeth to restore by participant will be of maximum of 6 and a minimum of one NCCL, within this clinical trial. The allocation of the study arms (G1 to G6) to a particular tooth is randomly allocated, with the information available to the operator/principal investigator in sealed envelopes and previously prepared by the investigator-statistics. The allocation of the study arms (G1, G2, G3, G4, G5, G6) to each tooth by participant is performed randomly, but ensuring that the distribution of the groups is not repeated in the same participant. For this purpose, will be organized by the statistical investigator, 210 envelopes with 35 sequences of 6 study arms, where in each order of 6 groups is randomized.

If the patient has more than six teeth that meet the inclusion criteria, the selection of the PM and M teeth to be included in the clinical trial will be conducted randomly by scenarios randomized by the statistical investigator after participation and contact for the effect (not done a priori, since it is necessary 19448 scenarios prior randomization before observing any patient, whereas the possible teeth to be selected for treatment is between 6 and 16 and the teeth to select from 6).

The participant has as cost the academic/scientific fees, as in usual clinical context of Dentistry School Clinic of **Sector Sector** as "restoration of a tooth surface"/ by tooth to restore (One to six teeth), which of course would have to make even not participating in the investigation, as the Dentistry School Clinic fee scale.

The restorations included in this trial will be evaluated for determine clinical performance from baseline to 24th month by the three calibrated examiners. These observation appointments (three, in two years) as part of the clinical trial will be free of charges for participants. Baseline and 24th month data will be statistically analysing, according to this trial purpose and hypothesis.

2.3-STUDY ADHESION ARMS

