	marginal quality or proximal contacts;	5.4.2
	bulk fractures with or without partial	Chip fracture damaging margins
	loss(less than half of the restoration)	5.4.3
		Notable enamel or dentine wall fracture
5. Clinically poor (replacement	4.5. Parcial or complete loss of restoration	5.5
necessary)		Filling is loose but in situ.
Acceptable or not acceptable (n, %, and reasons)	
Adapted from (33)		

c) BIOLOGICAL PROPERTIES	6. Postoperative Hipersesibility, tooth vitality	7. Recurrence of Caries, erosion, abfraction	8. Tooth integrity (enamel cracks)
1. Clinically excellent/ very good	6.1 No hipersensitivity, normal vitality	7.1 No secondary or primary caries	8.1 Complete integrity.
2. Clinically good (after correction, very good)	6.2 Low hipersensitivity for a limited period of time, normal vitality.	7.2 Very small and localized1. Demineralization2. Erosion or3. Abfraction.No operative treatmentrequired	8.2.1 Small margin enamel(<150 μm) 13.2.2 Hairline crack in enamel (<150 μm not probable)
3. Clinically sufficient/ satisfactory (minor shortcomings with no adverse effects but not adjustable without damage to the tooth)	 6.3.1 Premature/slightly more intense 6.3.2 Delayed/weak sensitivity; no subjective complaints, no treatment needed. 	 7.3.Larger areas of 1.Desmineralisation 2.Erosion 3. Abrasion/abfraction in dentine Localized and acessible and can be repaired 	8.3.1 Enamel split(<250 μm) 8.3.2 Crack < 250 μm, no adverse effects.
4. Clinically unsatisfactory (repair for prophylactic reasons)	6.4.1 Premature/very intense 6.4.2 Extremely delayed/weak with subjective complaints 6.4.3 Negative sensitivity intervention necessary but not replacement	7.4.1Caries with cavitation 7.4.2 Erosion in dentine 7.4.3 Abrasion/abfraction in dentine Localized and accessible and can be repaired	 8.4.1 Major enamel split (gap>250 μm or dentine or base exposed) 8.4.2 Crack>250 μm (probe penetrates).
5. Clinically poor (replacement necessary) Acceptable or not acceptable (n, %, and read	6.5 Very intense, acute pulpitis or no vital.Endodontic treatment is necessary and restoration has to be replaced.	7.5 Deep secondary caries or exposed dentine that is not accessible for repair of restoration.	8.5 Cusp or tooth fracture.
Acceptable or not acceptable (n, %, and rea Adapted from (33)	(SUIIS)		

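### Postoperative sensitivity is measured from a 30-day post-treatment value and arms are compared only at 24 months, so early sensitivity that settles can read as within-arm improvement

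*Combined protocol and SAP*

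**What the plan says.** Section 2.1 fixes the reference visit: "Baseline clinical observation will be done 30 days after placement of adhesion restoration". The 12-month visit is held, but its results are "data not to be included on final report". Section 2.2 confirms which visits count: "Baseline and 24th month data will be statistically analysing".

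Under section 2.7, changes in the clinical parameters on both scales "will be assessed by McNemar or Wilcoxon tests", for primary and secondary outcomes, from that visit to 24 months. The section describes these paired tests as showing how the treatments differ. Arms are tested against each other by Kruskal-Wallis, then Bonferroni-corrected Mann-Whitney tests, "Whenever 3 groups will be compared at 24 months' recall". The chi-square test in the same section compares the two scales, not the arms. No between-arm test at 30 days is specified.

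Postoperative sensitivity is one of the biological items on each scale (FDI item 6 in Annex 3; USPHS in Annex 4). Sections 2.5 and 2.6 apply the same air test one week before restoration and at every recall, and the clinical file in Annex 2 has a pre-operative column for it. Section 2.7 does not mention the pre-operative result.

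For missing data, including loss of retention, section 2.7 limits the baseline side of the paired comparison to restorations still present at 24 months.

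**The concern.** Sensitivity differs from most other scored items because the procedure itself can cause it and it can fade. Annex 3 recognises this in its second grade: "6.2 Low hipersensitivity for a limited period of time, normal vitality". The Introduction lists "the perception that SE adhesives cause less postoperative sensitivity than ER adhesives" among the reasons for the growing use of self-etch products, and adds that some of those reasons are disputed. A difference between adhesion modes in early sensitivity is therefore a plausible finding in this trial.

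If the 30-day score is the starting value, sensitivity present at that visit enters as the arm's initial condition and its settling is counted as improvement. The more early sensitivity an arm has, the more room it has to improve. At 24 months, when arms are compared, short-lived sensitivity would be expected to have gone. The plan would collect the data that show the difference, use them only as a reference value, and possibly report a significant gain for the arm that did worse.

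**Working it through.** **Inputs from the documents.** 35 restorations per arm in six arms (6 × 35 = 210, which reproduces the minimum in sections 2.2 and 2.8); significance at 0.05, taken as two-sided because the sidedness is not stated; paired tests from day 30 to 24 months; arm comparisons at 24 months. Section 2.8 cites at least 80 cases for a McNemar test but gives no discordance rates, so no event rate can be recovered from it.

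**Assumed.** Sensitivity rates, since the documents give none. In the simplest case everything sensitive at day 30 has resolved by 24 months and nothing is new.

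**Paired test within one arm.** With k restorations resolving and none new, the exact two-sided McNemar p-value is 2 × 0.5^k. An exact Wilcoxon signed-rank test with k changes all in one direction gives the same value.

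| k of 35 | % | p |
|---|---|---|
| 1 | 2.9 | 1.0 |
| 5 | 14.3 | 0.0625 |
| 6 | 17.1 | 0.031 |
| 7 | 20.0 | 0.016 |
| 8 | 22.9 | 0.0078 |

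With one new case at 24 months, 7 resolving give p = 0.070 and 8 give p = 0.039.

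**Chance of a significant improvement.** This is P(X ≥ 6), with X binomial on n pairs and true day-30 sensitivity π. The column for n = 28 shows the effect of fewer pairs at 24 months.

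| π | n = 35 | n = 28 |
|---|---|---|
| 5% | 0.7% | 0.2% |
| 10% | 13% | 5.5% |
| 15% | 43% | 24% |
| 20% | 73% | 50% |
| 30% | 97% | 89% |

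**The same arms compared directly.** Suppose one arm has 8/35 sensitive at day 30, another has 1/35, and both have none at 24 months.
- Paired tests: p = 0.0078 for improvement in the first arm, p = 1.0 in the second.
- Planned 24-month comparison: 0/35 against 0/35, no difference.
- Fisher's exact test at day 30, not planned: p = 0.028. With 7/35 against 1/35 it would be p = 0.055.

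**Retention.** Suppose 8/35 against 0/35 restorations are lost in the first month and none later. Over all restorations placed, 24-month retention is 27/35 against 35/35, Fisher p = 0.005. Over only those present at day 30 it is 27/27 against 35/35, no difference. The plan does not say which denominator applies.

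**Independence.** Section 2.2 does not repeat an arm within a participant, so pairs within an arm come from different participants. A participant may contribute up to six restorations across arms, so the Fisher p-values, which treat arms as independent, are illustrative.

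**The case against.** **The trial's question is at 24 months.** The overarching goal and the arm hypotheses concern performance at that time. If sensitivity has gone in every arm by then, a finding of equality is correct. This stands. A reader might infer that the worse arm would look better in the arm comparison; it would look equal. The apparent improvement exists only in the within-arm tests. It matters because section 2.7 offers those tests as evidence of treatment differences.

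**A post-placement reference is unavoidable.** Retention, margins, staining, colour and luster cannot be scored before a restoration exists. This stands, and confines the point to sensitivity, one of eight items on each scale in the clinical file.

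**Using within-arm tests to judge treatments is a flaw whatever the baseline date.** True, but for sensitivity the date also gives the arm with more early sensitivity the greater scope to improve.

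**Sensitivity at day 30 need not come from the adhesive.** Correct: it may be residual pre-operative sensitivity. A reader might also infer that no pre-treatment measurement exists. One does, by the same air test; it is simply unused.

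**Early loss.** A reader might infer that a restoration lost before day 30 is carried as a starting state and shows no change. The documents do not support this. Section 2.7 removes lost restorations from the paired comparison whenever the loss occurs, so that effect comes from the missing-data rule rather than the baseline date. A loss can still be scored at 24 months as missing (USPHS) or as FDI 4.5. What remains open is the undefined denominator for retention and success.

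**Conclusion.** The concern holds for postoperative sensitivity. The paired analysis starts from a post-treatment value and the specified arm comparisons are at 24 months only, so an arm with more sensitivity at day 30 can show a significant within-arm improvement while appearing equal to the others at the end.

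In an arm of 35 with complete resolution and no new cases, six sensitive restorations are enough and five are not. How likely this is depends on rates the documents do not give: from under 1% at a true day-30 rate of 5% to 97% at 30%. At low rates the problem is unlikely to arise; at 15 to 20% it is a realistic prospect. Sensitivity that begins and ends before day 30 has no scheduled assessment and is missed altogether.

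For retention the 30-day baseline is not the fault. The gap there is that lost restorations leave the paired comparison and no denominator is stated. The correction is worth making because it is cheap and uses data already planned.

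**What to change.** In section 2.7:

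1. Compare the arms directly on sensitivity (FDI item 6, USPHS sensitivity, air test) at the 30-day visit, as a labelled secondary analysis that takes account of the pre-operative air test and of participants contributing to several arms. State that change in sensitivity from 30 days to 24 months is descriptive and is not read as treatment performance. Substituting the pre-operative value as baseline in the within-arm tests would not be enough, since those tests still do not compare arms.
2. Compute 24-month retention and success over all restorations placed, counting every known loss, including those before day 30, as a failure. State separately how restorations not observed at 24 months are handled.

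The cost is wording plus one added secondary comparison per sensitivity item; no visit or measurement is added. The 30-day comparison has limited power. For 20% against 5% with 35 per arm, treated as independent: pooled rate 0.125, null standard error √(2 × 0.125 × 0.875 / 35) = 0.0791, alternative standard error √((0.20 × 0.80 + 0.05 × 0.95) / 35) = 0.0770, and power Φ((0.15 − 1.96 × 0.0791) / 0.0770) ≈ 47%. Report estimates with confidence intervals, and do not take a non-significant result as showing equal sensitivity.
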